programmed to connect users with a trainer via an app. We will recruit individuals between the ages of 30-55 years ($N = 20$) from a well-characterized cohort of adults in Jamaica with early-childhood exposure to malnutrition and other forms of ELA (e.g., poverty) confirmed by contemporaneous medical records who continue to participate in research led by Co-Investigators and Reversibility Network members [name] and [name]. A comparison sample ($N = 20$) of age, sex, and race matched adults with an ELA history will be recruited in Pittsburgh, and a harmonized battery of cognitive, fitness, and psychosocial measures will be collected in both samples at baseline and following the 12-week intervention.

We have assembled a highly creative, productive, and interdisciplinary team with extensive experience conducting exercise interventions and evaluating indicators of brain health in multiple vulnerable populations (e.g., older adults with cognitive impairment, adults with a history of malnutrition). We will test the following aims:

Aim 1: Determine the feasibility and acceptability of a remote PA intervention among adults exposed to threat-related ELA living in Pittsburgh and Jamaica. It is hypothesized that the remote format of the intervention will enhance the feasibility of conducting a PA trial among individuals with a history of threat-related ELA.

Aim 2: Determine whether the remote PA intervention promotes improvements in cognitive and psychological functioning. It is hypothesized that cognitive and psychological functioning will improve over the course of the intervention and improvements will be greatest among those with the highest adherence rates.

The proposed research addresses the central goal of the NIA Reversibility Network to develop and test feasible interventions that may mitigate ELA-related risk for adverse health outcomes in adulthood. This pilot feasibility trial will set the groundwork for a larger-scale future R01 application that will test the efficacy of a remote PA intervention for improving brain health among adults who have been exposed to ELA. Further, the proposed research will provide an initial test of the impact of country-level factors (e.g., poverty rates, prevalence of more severe ELA such as malnutrition) on ELA-related disease burden in adulthood, information which may be leveraged to tailor interventions to meet the specific needs of the target population.

1.1 Overview of Methods:

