1.1.1. Subject recruitment, Pittsburgh: We expect to advertise through numerous outlets in order to enhance our ability to successfully recruit for the study. Participants ($N=20$) will be recruited via methods found to be effective in other studies, including the University of Pittsburgh online research registry (Pitt+Me) and community presentations at local community centers. We will also advertise on the Brain Aging and Cognitive Health (BACH) lab website (<http://bachlab.pitt.edu/>), lab social media accounts (Facebook & Instagram), and will post flyers and other ads around the Pittsburgh community.

1.1.2. Subject recruitment, Jamaica: Participants ($N=20$) will be recruited from across Jamaica, particularly from the areas within and surrounding Kingston, Jamaica where the University of the West Indies is located. Participants will be age, sex, and race matched across sites.

1.1.3. Eligibility criteria: Inclusion criteria will be as follows: 1) adults aged 30-55 years, 2) exposure to at least one form of threat-related ELA (e.g., exposure to violence; physical abuse) prior to the age of 10 as documented by retrospective self-report (described in detail below), 3) self-identified Black or African American race, 4) access to high-speed internet, and 5) sedentary lifestyle (<60 minutes of PA/week). Exclusion criteria will include: 1) psychosis, 2) significant suicide risk (i.e., current, active suicidal ideation with a plan), 3) engaging in moderate-intensity exercise >=20 min per day, >=3 times per week, 4) current treatment for cancer, 5) neurological condition (e.g., MS, Parkinson's, Dementia, MCI) or brain injury (e.g., stroke), 6) substance use disorder in the past 3-months, 7) current treatment for congestive heart failure, angina, uncontrolled arrhythmia, DVT or other cardiovascular event, 8) myocardial infarction, coronary artery bypass grafting, angioplasty or other cardiac condition in the past year, 9) sensory impairment that would preclude neuropsychological testing, 10) not fluent in English, 11) travelling consecutively for 2+ weeks during the study, 12) uncontrolled hypertension, 13) insulin-dependent Diabetes Mellitus, and 14) self-identified as any race other than Black or African American.

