Aim 3: Attendance and adherence rates, as well as participant satisfaction ratings, will be compared using Paired sample T-tests to determine whether there are differences in these metrics across sites. Statistical tests performed to assess Aim 2 will be repeated separately for each site to evaluate whether effect sizes differ by site.

1.3. Minimization of Risks:

1.3.1. To reduce the risk for breach of confidentiality we will separate all information obtained during the screening period from identifying documents. All research data will be de-identified. These documents will be stored in a separate location from the data and the screening information in locked filing cabinets in a locked and secure room that only lab personnel have access to. Data that is saved electronically (computer system) is protected by the University of Pittsburgh firewalls. Regarding heart rate data collected via the Polar app, these data will only

be stored on the app temporarily (i.e., during the exercise session) in order to continuously monitor safety. This information will be transferred to our secure server as soon as possible after each session to minimize risk of breached confidentiality.

- 1.3.2. Subject privacy will be maintained in this research study by having all participants answer questions and perform cognitive tasks in an isolated and private room. All of the information that we will collect in this protocol is essential for the research questions we are posing. In this way, there will be no unnecessary personal information collected from these participants.

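### Two countries with one study centre each cannot test the impact of country-level factors on ELA-related disease burden, and the SAP plans no analysis that would

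*Combined protocol and SAP*

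**What the plan says.** The closing paragraph of section 1.0 states that the study "will provide an initial test of the impact of country-level factors" (the examples given are "e.g., poverty rates, prevalence of more severe ELA such as malnutrition") "on ELA-related disease burden in adulthood". It adds that this information could be used to adapt interventions to the population being served.

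The design has 20 participants in Jamaica and 20 in Pittsburgh. Section 1.0 takes the Jamaican group from an established research cohort with medically documented early malnutrition. Section 1.1.2 describes participants who "will be recruited from across Jamaica, particularly from the areas within and surrounding Kingston". For the United States, a comparison sample "of age, sex, and race matched adults with an ELA history will be recruited in Pittsburgh"; section 1.1.1 lists an online research registry, community presentations, social media and flyers as the routes. Section 1.1.3 requires of everyone "exposure to at least one form of threat-related ELA (e.g., exposure to violence; physical abuse) prior to the age of 10".

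The SAP (section 1.2) covers feasibility and acceptability under Aim 1 and paired t-tests of pre-post change in cognitive and psychological functioning under Aim 2. Aim 3 compares attendance, adherence and satisfaction "to determine whether there are differences in these metrics across sites" and repeats the Aim 2 tests within each site to see whether effect sizes differ.

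**The concern.** The sentence in section 1.0 promises a test of a cause that operates at country level on an outcome called disease burden. Neither the sampling nor the SAP supplies what such a test needs: enough countries to distinguish one country characteristic from another, a designated burden outcome, and an analysis linking the two.

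What is at stake is interpretation. The same section says the pilot will lay the groundwork for a larger R01 application. A difference between Pittsburgh and Jamaica could be carried into that application as evidence about poverty or malnutrition when it may equally reflect how, where and by whom participants were recruited and followed.

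**Working it through.** The documents give no sample size derivation or power figure for this claim, so there is nothing to reproduce. The check is one of identifiability, followed by a comparison of the claim with the rest of the plan.

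**Inputs.** Two countries, with one institution named in each (section 1.0 and sections 1.1.1 to 1.1.2); 20 participants per country, 40 in total; two example country-level factors, poverty rate and malnutrition prevalence (section 1.0).

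**Step 1: one country-level factor.** At country level the model is: country mean = b0 + b1 × factor. Two countries give 2 data points and the model has 2 parameters, so the residual degrees of freedom are 2 − 2 = 0. The line passes through both points whatever the data are. Nothing is left over to judge whether the factor explains the difference.

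**Step 2: two country-level factors.** Let J = 0 for Pittsburgh and 1 for Jamaica. Any factor with value a in one country and b in the other equals a + (b − a) × J. With arbitrary illustrative values of 0.3 and 0.9, the factor is 0.3 + 0.6 × J. A design matrix for all 40 participants with an intercept, J and this second factor has 3 columns but rank 2. Poverty rate and malnutrition prevalence are therefore the same variable up to scale. So is every other characteristic that differs between the sites and is constant within them: staff, recruitment route, source cohort.

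**Step 3: more participants.** If countries differ for unrelated reasons with variance σc², and participants within a country vary with variance σ², the difference between two country means from n participants each has variance 2(σc² + σ²/n). As n grows this falls only to 2σc², and two countries give no means of estimating σc² separately from the effect of the factor. Enlarging the sites does not repair the design.

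**Step 4: what the sampling fixes.** If the Jamaican sample comes from the malnutrition cohort, as section 1.0 says, the frequency of malnutrition in it is set by cohort selection and not by national prevalence. Matching covers age, sex and race only.

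**Step 5: the outcome.** Section 1.0 describes ELA-related burden as psychiatric disorder, type II diabetes, obesity, cardiovascular disease, cognitive decline and Alzheimer's disease. No variable is designated to represent it. Health history is collected to decide eligibility (section 1.1.6.2). The exclusions in section 1.1.3 include psychosis, recent substance use disorder, dementia, mild cognitive impairment, stroke, treated or recent cardiac disease, uncontrolled hypertension and insulin-dependent diabetes; section 1.3.6 adds any history of heart disease. Much of the burden is thus screened out at both sites, though obesity, depressive symptoms and anxiety are not.

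**Step 6: the analysis.** Section 1.2 contains no country-level covariate, no comparison between countries of the level of any health measure, and no ELA-by-country term. Aim 3 addresses engagement, satisfaction and site-specific change over 12 weeks of exercise. None of these is a measure of disease burden by country.

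**The case against.** The sentence opens as an additional benefit, says only that the test is initial, and is not one of the aims listed in section 1.0. Section 1.2 states that the study is a feasibility pilot. Aim 3 speaks of sites and attributes nothing to country. All of this stands, and it limits the weight of the point. It does not rescue the sentence: an initial test is a weak test, and here there is none. The disclaimer about power in section 1.2 concerns effectiveness of the intervention, not this claim.

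Several stronger readings are tempting, and the documents do not support them:

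- *Because everyone is exposed, there is no ELA effect to compare.* Section 1.1.6.1 forms a composite score for degree of exposure and plans exploratory analyses by ELA type, so a severity gradient exists within the sample. What is missing is a planned analysis of that gradient by country.
- *The comparison of attendance, adherence and satisfaction is the only related analysis.* Aim 3 also repeats the Aim 2 tests by site.
- *Nothing measured bears on disease burden.* Depressive symptoms, anxiety, cognition and BMI could act as proxies. The plan does not designate them as such and does not compare their levels between countries.
- *The problem is that 20 per site is too imprecise.* Precision calculations for unpaired means or for proportions would not match Aim 3, which specifies paired tests and no binary outcome. Identifiability fails at any sample size in any case.
- *Each country contributes a single locality.* Section 1.1.2 recruits across Jamaica; the limit is one study centre per country.

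**Conclusion.** The concern holds as a mismatch between a stated property and the design, at minor severity. With two countries, a country-level factor leaves zero residual degrees of freedom and cannot be told apart from any other difference between the sites. This follows from the structure alone and needs no assumption about alpha, variance or effect size. It rests on reading the documents as having one study centre per country, which is all they describe. The absence of a designated burden outcome, and of any between-country or ELA-by-country analysis of it, is a second and separate gap; filling it would still leave the first.

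A reader might infer that the site comparison in Aim 3 is worthless or that the pilot's main purpose is compromised. Neither follows. A descriptive contrast between the two sites is useful for planning, and the feasibility and acceptability aims do not depend on the sentence.

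**What to change.** In section 1.0, either delete the sentence or replace it with wording such as: *The study will also provide a descriptive, hypothesis-generating comparison of feasibility, acceptability and site-specific pre-post change between the two sites.*

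In section 1.2, Aim 3, add: *Differences between sites will be reported as estimates with 95% confidence intervals and will not be attributed to country-level factors.*

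The cost is two sentences. Recruitment, assessments, outcomes and sample size are unchanged. The sponsor gives up a claim that the data could not support.

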1.1.9. Activity monitoring: At the end of the baseline assessment visit, eligible participants will be fitted with a commercially available physical activity monitoring device (ActiGraph Link), worn on the wrist. ActiGraph Link provides information about movement, rotation, and body position, that is used to determine intensity and amount of physical activity. Activity monitoring will be completed one-week prior to and one-week after completion of the intervention.

1.1.10. Exercise training session: After completion of the initial assessment visit and the activity monitoring period, two study team members will schedule a time to transport a study stationary bike to the participant's home via a university-owned vehicle, set-up the bike in the participant's home, and monitor the participant's first home-based exercise session in-person. Participants will also be provided with a study-owned tablet loaded with the application (described below) that will be used to administer and monitor their exercise regimen throughout the intervention.

1.1.11. Participants will complete one onsite exercise session, during which they will work with the exercise physiologist to determine the appropriate peddling speed corresponding to a moderate-intensity exercise zone based on the American College of Sports Medicine Guidelines. Heart rate and blood pressure will be monitored during this session to ensure that the participant does not exceed ACSM guidelines for safe activity.

1.1.12. Exercise intervention: The intervention will use personalized physical activity regimens that are remotely administered by exercise staff using an application called Neotiv. Neotiv has been programmed by a research group in Germany who have agreed to make it freely available for this pilot study. Neotiv is integrated with the stationary bike, allowing for the collection of data about speed, resistance, and duration of cycling. We will use Neotiv to monitor adherence to the intervention protocol and to adjust the protocol as needed. The participant will complete three exercise sessions per week on the bike at home for 12-weeks, which will gradually increase in duration from 15- to 50-minutes over the first month of the intervention. The final weekly exercise goal will be set to 150 minutes.

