A study team member will check-in with participants via weekly emails or calls with participants via phone or HIPAA-compliant videoconferencing software to troubleshoot issues that arise during exercise, discuss participants' subjective exercise experience, and problem-solve barriers to adherence. The format of these check-ins will be determined by the participant's preference, progress, and needs, and may change over the course of the intervention as warranted. Exercise safety will also be reviewed during these weekly check-ins and participants will be encouraged to reach out to the study staff if any safety-related concerns arise. Participants will also be asked about whether there have been any issues with their bike or other equipment. Should damage occur, two staff people will schedule a time to visit the participants home to fix the issue(s) noted or to collect the bike to be returned to the manufacturer for repair. In the event that the bike must be returned to the manufacturer for repair, participants will be furnished with a replacement bike within 5 days of the removal of the original bike, and any exercise sessions missed as a result will either be made up within the following week or marked as absences that will not be counted toward the participant's attendance/adherence bonus numbers.

1.1.13. Follow up assessment: All of the baseline assessments will be repeated at follow-up after completing the 12-week intervention, including cognitive and psychological functioning, and physical activity monitoring (see descriptions above). We will not administer CTQ or MACE questionnaires at follow-up given that scores on these questionnaires should not change.

1.1.14. Bike return: Following the completion of the 12-week intervention, the study PI and a staff member will return to participants' homes to collect the study-issued

stationary bike, tablet, and heart rate monitor. Any needed repairs will be made and equipment will be cleaned for use by another participant.

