1.2. Statistical Analysis Plan: This intervention is a pilot feasibility investigation. Therefore, the primary focus is on evaluating how successful we are at recruitment and retention, and whether we are able to keep participants engaged in the intervention. Although we will evaluate the effect of the intervention on cognitive and psychological functioning, is not intended to be statistically powered to address questions regarding the effectiveness of the intervention for improving the outcomes among adults exposed to early life adversity.

Aim 1a. The feasibility of this intervention will be assessed by examining average adherence rate over the course of the intervention, operationalized as a combination of number of sessions attended and average duration of each session. Average number of minutes spent in the 'moderate-intensity' heart-rate zone per session will also be examined. Threshold analysis will be conducted to understand whether exercise adherence declines after a certain time point in the intervention (e.g., 6-weeks). In an exploratory analysis, ActiGraph data will be used to assess whether engagement in the intervention results in an increase in physical activity from pre- to post-intervention.

Aim 1b. Intervention acceptability will be assessed through a self-report questionnaire completed post-intervention, including questions about satisfaction with various aspects of the intervention (i.e., intervention duration, interaction with study staff, use of technology to remotely guide intervention, overarching feedback about intervention, willingness to continue engaging in exercise).

Data related to 1) study enrollment and 2) summaries of weekly video/phone calls to monitor exercise adherence and engagement will be documented. The recruitment process (e.g., proportion of participants screened who enrolled in the study) and participants' experience in the intervention based on weekly phone sessions and the satisfaction questionnaire at the completion of the study will be qualitatively examined.

Aim 2. Paired sample T-tests will be used to assess change in cognitive and psychological functioning over the course of the 12-week intervention.

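### Follow-up measures and the satisfaction form are timed to completing the exercise programme, with no provision for participants who stop early, so Aims 1b, 2 and part of 3 would rest mainly on completers

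*Combined protocol and SAP*

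**What the plan says.** Everything measured after the exercise period is timed by reference to its end:

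- **Section 1.1.13 (cognitive, psychological and activity measures):** "All of the baseline assessments will be repeated at follow-up after completing the 12-week intervention".
- **Section 1.1.9 (activity monitor):** "Activity monitoring will be completed one-week prior to and one-week after completion of the intervention".
- **Section 1.2, Aim 1b (acceptability):** "Intervention acceptability will be assessed through a self-report questionnaire completed post-intervention". Later under the same aim: "participants' experience in the intervention based on weekly phone sessions and the satisfaction questionnaire at the completion of the study will be qualitatively examined".
- **Section 1.2, Aim 2:** "Paired sample T-tests will be used to assess change in cognitive and psychological functioning over the course of the 12-week intervention".

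Aim 3 compares satisfaction between sites and repeats the Aim 2 tests within each site, so it inherits whatever follow-up exists.

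The documents do not define completion of the intervention. They describe no week-12 or early-termination assessment for someone who stops, name no analysis set, and give no method for missing follow-up. Sections 1.3.6 and 1.3.7 foresee that exercise may be interrupted or stopped, but do not say what then happens to outcome assessment.

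**The concern.** Section 1.2 makes recruitment, retention and engagement the main focus of this pilot, and Section 1.0 explains why this population may find it hard to stay in a trial. Participants who stop are therefore central to the question. They are the people best placed to say why the remote format did not work, yet nothing in the plan secures a satisfaction rating or a week-12 outcome from them.

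Three results are exposed:

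- A paired t-test uses only participants with both a baseline and a follow-up value. If stoppers have no follow-up, Aim 2 describes those who finished.
- Acceptability is rated only by those who finished.
- If dropout differs between Pittsburgh and Jamaica, the Aim 3 comparisons of satisfaction and of pre-post change could show a site difference that reflects who remained, or could hide a real one.

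The second Aim 2 hypothesis is that improvement is largest in the most adherent. Losing the least adherent participants narrows the range of adherence over which that can be examined.

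**Working it through.** **Inputs from the documents.** Section 1.1.1: "Participants ($N=20$) will be recruited via methods found to be effective in other studies". Section 1.1.2: "Participants ($N=20$) will be recruited from across Jamaica". The total is 20 + 20 = 40. The documents state no dropout rate, effect size, SD or expected satisfaction, so there is no figure of the plan's own to reproduce. All values below other than 40 and 20 are assumptions, shown over a range.

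**Numbers left.** With dropout proportion d, participants with follow-up = N(1 − d). At d = 20%, 30% and 40% this gives 32, 28 and 24 of 40 overall, or 16, 14 and 12 of 20 per site.

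**Aim 2 change.** Let C be the mean change in completers and S the mean change in stoppers, in SD units and signed so that positive means benefit.

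- All-enrolled mean = (1 − d)C + dS
- Completer mean minus all-enrolled mean = d(C − S)

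With C = 0.30:

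| Assumed S | d = 20%: all-enrolled (bias) | d = 30% | d = 40% |
|---|---|---|---|
| 0 | 0.24 (+0.06) | 0.21 (+0.09) | 0.18 (+0.12) |
| 0.15 | 0.27 (+0.03) | 0.255 (+0.045) | 0.24 (+0.06) |
| 0.30 | 0.30 (0) | 0.30 (0) | 0.30 (0) |
| 0.40 | 0.32 (−0.02) | 0.33 (−0.03) | 0.34 (−0.04) |

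In the first row the completer figure exceeds the all-enrolled figure by 25%, 43% and 67% (0.30/0.24 = 1.25, 0.30/0.21 = 1.43, 0.30/0.18 = 1.67). The sign depends entirely on whether S is below or above C.

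**Aim 1b acceptability.** For illustration, treat satisfaction as yes or no and assume 80% of completers are satisfied. With a proportion s of stoppers satisfied, the all-enrolled proportion = 0.80(1 − d) + d·s.

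| d | s = 0 | s = 0.40 | s = 1 |
|---|---|---|---|
| 20% | 64% | 72% | 84% |
| 30% | 56% | 68% | 86% |
| 40% | 48% | 64% | 88% |

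The observed 80% would be too favourable if stoppers are less satisfied, which is plausible. Without their ratings, however, the data allow values on either side of 80%.

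**The case against.** A reader might infer that the plan restricts its analysis to completers. The documents do not say so. The wording in 1.1.13 can be read as timing only. Section 1.1.14 uses a similar phrase for collecting the bike, and bikes would presumably be collected from people who stop as well. Sections 1.0 and 1.1.8 describe the second assessment simply as following the intervention, and one sentence under Aim 1b ties the satisfaction form to the end of the study. This stands: a completer-based result is the likely consequence of following the text literally, not a stated rule. But two sites must apply the text alike, and it does not tell them what to do when someone stops.

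A reader might also infer that the results are certainly biased upward. That does not follow. The direction comes from the protocol's adherence hypothesis, and the table shows zero or reversed bias under other assumptions. The word upward would also mislead for the stress, anxiety and depression scales, where lower scores are better.

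Nor is it right that the adherence hypothesis could no longer be examined. Adherence combines sessions attended and session duration, so it still varies among participants with follow-up. The range is narrowed, not removed.

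Finally, the plan does learn something about people who later stop, from weekly check-ins, mood and exertion ratings at each session, and app data on adherence. Retention and adherence themselves need no follow-up visit. This also stands, but these sources run only until the person stops. The check-ins are summarised qualitatively, and none of these sources supplies the satisfaction rating compared in Aim 3 or a week-12 cognitive or psychological score.

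**Conclusion.** The point holds as a gap in planned data collection. Post-intervention outcomes and the satisfaction form are timed to completion, and nothing provides for people who stop. Followed literally, Aim 1b, Aim 2 and the parts of Aim 3 built on them would rest mainly on completers. If the protocol's hypothesis about adherence is right, Aim 2 change is probably biased toward benefit; acceptability would probably look better than it is if stoppers are less satisfied.

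The size cannot be derived from the documents. On assumed changes of 0.30 SD in completers and 0 in stoppers, the excess is 0.06 to 0.12 SD at 20% to 40% dropout. It disappears if stoppers change equally. The study is not powered for effectiveness, so the matter bears on how its feasibility and pre-post results are interpreted, not on a confirmatory test.

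**What to change.** - **Section 1.1.13 and Aim 1b:** state that everyone who starts the intervention is invited to the follow-up assessment and the satisfaction questionnaire 12 weeks after starting, whether or not they are still exercising. Align the timing in 1.1.9.
- **Participants who will not attend:** send the REDCap questionnaires remotely. Section 1.1.7 already uses survey links for the psychological scales. The cognitive tests still need a visit.
- **Aim 2:** define the population as all participants with baseline and week-12 data regardless of adherence. Define completion, and give the completer analysis as secondary.
- **Reporting:** by site, give the number assessed and the baseline scores of those without follow-up. Some people who stop will decline assessment, so the reader needs this to judge what remains missing.

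**Cost.** Protocol and SAP wording; some effort to contact people who have stopped; at most one follow-up visit per enrolled participant, 40 in all; and possibly less favourable results. If the sponsor already intends to assess everyone, only the wording changes.
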